### **2.3.2 Benefit Assessment**

Patients with severe uncontrolled asthma, enrolled in this trial are expected to benefit from the benralizumab therapy for symptomatic relief, improved lung function, fewer exacerbations and fewer hospital visits. For enrolling in this study, the physician would have already determined the eligibility of the patient who would be prescribed and derive benefit from benralizumab. The cost of the study treatment will be borne by AstraZeneca for 4 doses. Data generated from this study will help evaluate the safety of benralizumab in clinical settings in India. It will help provide a safer alternative to patients with severe uncontrolled asthma, reducing their dependency on high doses of long-term systemic steroids.

### **2.3.3 Overall Benefit: Risk Conclusion**

Taking into account the overall benefit-risk profile of benralizumab, and the unmet need of the patients of severe asthma with eosinophilic phenotype, the anticipated benefits outweigh the risks for the participants in the study.

### 3 OBJECTIVES AND ENDPOINTS

Objectives and endpoints are provided in Table 2.

**Table 2 Objectives and Endpoints**

Primary Objective	Primary Endpoints
To assess the safety and tolerability of Fasenra (benralizumab) in adult patients of severe asthma with eosinophilic phenotype over a period of 24 weeks	

percentage of AEsa, SAEs, and TEAEs

nature, incidence, and severity of AEs including unexpected adverse drug reactions

percentage of patients with AEs that lead to study treatment discontinuations or modifications

Secondary Objective	Secondary Endpoints
To assess the effectiveness of Fasenra (benralizumab) in adult patients of severe asthma with eosinophilic phenotype over a period of 24 weeks	

time to first asthma exacerbationb

annualised exacerbation rate

overall investigator's assessment on the outcome of the treatment: "well controlled", "partly controlled", "uncontrolled"

change in blood eosinophil levels from baseline till Weeks 4, 16, and 24

Abbreviations: AE = adverse event; SAE = serious adverse event; TEAE = treatment-emergent adverse event

a AEs that are reported and observed

b where an asthma exacerbation is defined by a worsening of asthma requiring

- Use of systemic corticosteroids (or a temporary increase in a stable oral corticosteroid background dose) for at least 3 days; a single depot-injectable dose of corticosteroids will be considered equivalent to a 3 day course of corticosteroid OR
- An emergency room/urgent care visit (defined as evaluation and treatment for <24 hours in an emergency room or urgent care centre) due to asthma that required systemic corticosteroids (as per above) OR
- An inpatient hospitalisation due to asthma (defined as admission to an inpatient facility and/or evaluation and treatment in a healthcare facility for ≥24 hours).

## 4 STUDY DESIGN

### 4.1 Overall Design

This is a Phase 4, single-arm, prospective, multicentre, interventional study, designed to assess the safety, tolerability, and effectiveness of benralizumab in adult patients of severe asthma with eosinophilic phenotype in India. The study is planned to meet the postapproval commitment as a regulatory requirement.

Ten centres across India will participate in this study. The investigators will be pulmonologists or chest physicians treating asthma patients. Informed consent will be obtained from all the patients at screening before any study-related procedures are performed. Adult patients of severe asthma with eosinophilic phenotype, who are prescribed benralizumab as an add-on therapy by the treating physician, will be enrolled in the study.

The total study duration will be 24 weeks, including 16 weeks of study treatment, and 8 weeks follow-up ([Figure 1](#)).

- Screening duration: 2 weeks
- Study period: 24 weeks
  - Treatment duration (4 doses): 16 weeks (Day 1, Week 4, Week 8, and Week 16)
  - Post-treatment follow-up duration: 8 weeks (Week 24)

Benralizumab will be provided by AstraZeneca Pharma India Ltd. for the duration of the study.

Participants will be maintained on their currently prescribed therapies including ICS-LABA therapy(ies), throughout the study duration.

### 4.2 Scientific Rationale for Study Design

This proposed Phase 4 single-arm study will fulfil the regulatory requirement as a postmarketing study to assess the safety of 30-mg benralizumab administered subcutaneously in Indian patients of severe asthma with eosinophilic phenotype who remain uncontrolled on high doses of ICS plus LABA. Owing to the recent marketing approval, there are no data available from real-life studies in the Indian population. Participants included in this study will be as per the indicated patient profile in the local prescribing information, specifically taking into consideration the contraindications, warnings, and special precautions for use.

### 4.3 Justification for Dose

The study will enrol patients who have been prescribed benralizumab as per the local prescribing information. The recommended dose is 30 mg administered once every 4 weeks for the first 3 doses, and then once every 8 weeks thereafter by subcutaneous injection into the upper arm, thigh,

#### **4.4 End of Study Definition**

A participant is considered to have completed the study when he/she has completed his/her end of study (EOS) visit at Week 24, 8 weeks after end of treatment (EOT), as per the schedule of activities (SoA) in [Section 1.3](#).

The EOS is defined as the last expected visit of the last participant undergoing the study.

See [Appendix A](#) for guidelines about dissemination of study results.

## 5 STUDY POPULATION

Study population will include adult (18 to 75 years of age) male or female patients who have severe asthma with eosinophilic phenotype requiring high dose of ICS and LABA.

Each participant should meet all the inclusion criteria and none of the exclusion criteria to be eligible for the study. Under no circumstances can there be exceptions to this rule. Participants who do not meet the entry requirements are screen failures, refer to [Section 5.4](#).

“Enrolled” means a participant's, or their legally acceptable representative's, agreement to participate in a clinical study after completion of the informed consent process. Prospective approval of protocol deviations to recruitment and enrolment criteria, also known as protocol waivers or exemptions, is not permitted.

### 5.1 Inclusion Criteria

Patients are eligible to be included in the study only if all of the following criteria apply:

1. Male or female patients 18 to 75 years of age inclusive, at the time of signing the informed consent
2. Patients with physician's confirmed diagnosis of severe asthma with an eosinophilic phenotype, ie, diagnosis of severe asthma in preceding at least 12 months, with an eosinophil count of  $\geq 300$  cells/ $\mu$ L at screening, requiring treatment with high-dose ICS ( $>500$   $\mu$ g fluticasone propionate dry powder formulation, or  $>800$   $\mu$ g budesonide dry powder formulation, or equivalent total daily dose) and a LABA as maintenance treatment for at least 3 months prior to enrolment
3. A decreased lung function with prebronchodilator (Pre-BD) forced expiratory volume in 1 second (FEV1) of  $<80\%$  predicted, demonstrated by spirometry at screening
4. At least 2 documented asthma exacerbations in the preceding 12 months, except in 30 days before the date of informed consent, that required the use of a systemic corticosteroid or temporary increase from the patient's usual maintenance dose of OCS
5. Documented postbronchodilator (post-BD) reversibility in FEV1 of  $\geq 12\%$  and  $\geq 200$  mL in FEV1 within 12 months before first dose. If historical documentation is not available, reversibility must be demonstrated and documented at screening or Day 1 before first dose
6. Benralizumab naive patients who have not previously received benralizumab prior to the start of this study
7. Patients who are willing and capable of giving signed informed consent as described in [Appendix A](#), which includes compliance with the requirements and restrictions listed in the informed consent form (ICF) and in this protocol.

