The recent European Respiratory Society/American Thoracic Society guidance recommends anti-IL-5 and anti-IL-5R $\alpha$  agents for severe uncontrolled adult eosinophilic asthma phenotypes, and recognises the long-term safety of these therapies. The Global Initiative for Asthma (GINA) 2020 guidelines recommend add-on anti-IL-5 and anti-IL-5R $\alpha$  treatment for severe eosinophilic asthma that is uncontrolled on step 4-5 treatment (Evidence level A). The safety of benralizumab is well established based on the pivotal SIROCCO, CALIMA, and ZONDA trials. Integrated analyses (BORA) of approximately 1600 patients with asthma (about 1000 of whom were exposed to benralizumab for up to 2 years) suggest that eosinophil depletion by benralizumab treatment does not increase risk of infections or malignancies. The MELTEMI study (open-label safety extension study of BORA) reported that benralizumab was well tolerated and the most frequently reported treatment-emergent adverse events (TEAEs) were nasopharyngitis, asthma, headache, viral upper respiratory tract infection, and bronchitis, reported by 131 (29.4%), 55 (12.3%), 53 (11.9%), 48 (10.8%), and 45 (10.1%) patients, respectively (MELTEMI D3250C00037 clinical study report [CSR], 2020). The cumulative worldwide post-approval patient exposure to benralizumab since launch is estimated to be 79,307 patient-years, and the combined analyses of the cumulative efficacy and safety data available continue to indicate a positive benefit-risk balance of

Fasenra (benralizumab) has been recently approved in India with the condition to conduct a Phase 4 postmarketing study in the Indian population, as previous studies did not include patients from India. This prospective postmarketing safety study is planned to meet the regulatory mandate and assess the safety of benralizumab treatment in adult patients of severe asthma with eosinophilic phenotype over a period of 24 weeks. This interventional study will provide insights into the potential risks of eosinophil-lowering therapies when used in routine clinical care in India. The study will also evaluate the effectiveness of benralizumab in reducing asthma exacerbations.

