### **8.3 Effectiveness Assessments**

#### **8.3.1 Assessment of Asthma Exacerbations**

For the protocol, an asthma exacerbation will be defined as a worsening of asthma that leads to any of the following:

- Use of systemic corticosteroids (or a temporary increase in a stable OCS background dose) for at least 3 days; a single depot-injectable dose of corticosteroids will be considered equivalent to a 3-day course of systemic corticosteroids.
- An ER/Urgent care visit (defined as evaluation and treatment for <24 hours in an emergency department or urgent care centre) due to asthma that required systemic corticosteroids (as per above).
- An inpatient hospitalisation (defined as admission to an inpatient facility and/or evaluation and treatment in a healthcare facility for ≥24 hours) due to asthma.

Time to first asthma exacerbation will be calculated from baseline (Day 1) to time of first exacerbation. The start of an exacerbation is defined as the start date of systemic corticosteroids, ER or urgent care visits requiring systemic corticosteroids, or hospital admissions due to asthma, whichever occurs earlier. The end date is defined as the last day of systemic corticosteroids or ER/Urgent care/hospital discharge, whichever occurs later.

In order to calculate the number of exacerbations experienced by a patient during the study period, the following rule will be applied. The start of an exacerbation is defined as the start date of systemic corticosteroids or start date of a temporary increase in a stable OCS background dose, or start date of hospital admission, whichever occurs earlier. The end date is defined as the last day of systemic corticosteroids or the last day of a temporary increase in a stable OCS background

Version: 1.0 Dated 09 Mar 2021

dose, or the date of discharge from a hospital, whichever occurs later. Additional systemic corticosteroid treatments, ER/urgent care visits requiring use of systemic corticosteroids, or inpatient hospitalisation due to asthma occurring during an exacerbation should not be regarded as a new exacerbation. In order to be counted for as a new exacerbation it must be preceded by at least 7 days in which neither criterion is fulfilled.

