No	xx (xx.xx)	(xx.xx, xx.xx)
Missing	xx (xx.xx)	(xx.xx, xx.xx)
Visit x		
Patient Experience any new Exacerbation or change in existing Exacerbation since last visit		
Yes	xx (xx.xx)	(xx.xx, xx.xx)
No	xx (xx.xx)	(xx.xx, xx.xx)
Missing	xx (xx.xx)	(xx.xx, xx.xx)

- The Capital "N" in the column header represents the total number of Evaluable Analysis Set.
- The small "n" in summary statistics represents the total number of patients.
- All Percentages rows are based on the total number of Evaluable Analysis Set.
- 95% CI calculate will be using Clopper-Pearson Exact method.
- Programmer Note: Visit x- Visit 2, Visit 3, Visit 4 and Visit 5
- Source: Listing 16.2.1.1 and Listing 16.2.1.2

Document Title:	Document ID:	BP04-01
Statistical Analysis Plan	Version Number:	3.1
	Effective Date:	25-Nov-2021

Table 14.2.1.3. Summary of Before and After Treatment Exacerbation (Evaluable Analysis Set)

N = xx

**Exacerbation
before study**

N	xx
Missing	xx
Mean (SD)	x.x (x.xx)
Median	x.x
(min, max)	(x,x)
(25th Percentile, 75th Percentile)	(x.xx, x.xx)

**Exacerbation at
end of study**

n	xx
Missing	xx
Mean (SD)	x.x (x.xx)
Median	x.x
(min, max)	(x,x)
(25th Percentile, 75th Percentile)	(x.xx, x.xx)
P-value	x.XXXX

**Annualized
exacerbation
rate**

x.xx

- The column header's capital "N" denotes the total number of Evaluable Analysis Sets.
- The modest "n" in the number of patients suffering from exacerbation.
- The annual rate for each patient was calculated by dividing the total number of exacerbations by the number of days participated in the study and multiplying by 365.
- Source: Listing 16.2.2.1, Listing 16.2.2.2 and Listing 16.2.2.3

Document Title:	Document ID:	BP04-01
Statistical Analysis Plan	Version Number:	3.1
	Effective Date:	25-Nov-2021

Table 14.2.2. Summary of Time to first Exacerbation (Evaluable Analysis Set)

		N=xxx
Patient Asthma Exacerbation, n (%)		
Yes		xx(xx.xx)
No		xx(xx.xx)
Duration of Patient First Asthma Exacerbation (Days)		
n		Xx
missing		xx
Mean (SD)		xx.x (xx.xx)
Median		xx.x
(min , max)		(xx.xx, xx.xx)
(25 th Percentile, 75 th Percentile)		(xx.xx, xx.xx)
Estimate for Time to Response (Days)		
Median		xx.x
95 % CI		(xx.xx, xx.xx)

- The Capital "N" in the column header represents the total number of Evaluable Analysis Set.
- The small "n" in summary statistics represents the total number of patients
- Estimate for Time to Response using Kaplan-Meier method.

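### The SAP's before/after exacerbation table and its P-value cannot support a reduction due to benralizumab, because patients were selected on their exacerbation history

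*Protocol*

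**What the plan says.** The synopsis rationale (Protocol 1.1) states: "The study will also evaluate the effectiveness of benralizumab in reducing asthma exacerbations". The secondary endpoints in Protocol Section 3 are time to first exacerbation, annualised exacerbation rate, the investigator's overall assessment and change in blood eosinophils. Neither they nor the effectiveness analyses in Section 9.4.3 include a comparison with the pre-study period. Protocol 9.1 and SAP 6.2 say that no hypothesis is tested. Protocol 6.4 acknowledges that there is no control group.

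The SAP nevertheless has a mock table, 14.2.1.3, titled "Summary of Before and After Treatment Exacerbation (Evaluable Analysis Set". It has one block for exacerbations before the study, one for exacerbations at end of study with a P-value row, and a separate row for the annualised rate. SAP 6.3.2 names no test for it and does not describe it.

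Three further provisions bear on the comparison:

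- **Selection.** Inclusion criterion 4 requires "At least 2 documented asthma exacerbations in the preceding 12 months, except in 30 days before the date of informed consent", each event being one "that required the use of a systemic corticosteroid or temporary increase from the patient's usual maintenance dose of OCS".
- **On-study definition (Protocol 8.3.1).** The steroid limb is "Use of systemic corticosteroids (or a temporary increase in a stable OCS background dose) for at least 3 days", with one depot injection counted as equivalent. A separate limb is "An inpatient hospitalisation (defined as admission to an inpatient facility and/or evaluation and treatment in a healthcare facility" for at least 24 hours, with no steroid requirement.
- **Background therapy.** Inclusion criterion 2 requires high-dose ICS "and a LABA as maintenance treatment for at least 3 months prior to enrolment". Section 6.6.1 then asks for stable doses to the end of the study.

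**The concern.** Table 14.2.1.3 is the only place in either document from which a statement about reducing exacerbations could be drawn. If its fall and P-value are read as the drug effect, the reading is unsound for two main reasons. Patients enter because their prior count was high, so the later count is expected to be lower at many plausible rates even if the drug does nothing. The two periods also differ in length, and nothing in the SAP annualises the history.

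Two other differences make the periods less alike: the event definition, and possibly the background therapy. Section 6.4 mentions the missing control group but none of these. At stake is what the report can say on the secondary objective. The trial can describe a rate on treatment; it cannot attribute a change from history to treatment.

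**Working it through.** **The plan's own figure.** The only calculation in the documents is for adverse-event precision: n = 1.96² × 0.10 × 0.90 / 0.05² = 138.3, so 139; 139 / 0.95 = 146.3, so 147. Both reproduce. Neither concerns exacerbations, and no exacerbation rate or before/after effect is stated anywhere.

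**1. Unequal windows.** History covers 12 months (365 days); follow-up runs to Week 24 (168 days). At a constant rate, the expected raw count changes by 168/365 = 0.46, a fall of 54%. The table's footnote annualises events over days in the study, which serves the rate row; nothing does the same for history. The 54% assumes zero-event patients are in the end-of-study mean. The footnote describes n as the patients suffering an exacerbation; if zero-event patients were dropped, that mean would be biased upward instead.

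**2. Selection on the prior count, no drug effect.**

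Inputs from the protocol: 365 − 30 = 335 history days in which a qualifying event can fall. Exclusions 7 and 8 force an event-free gap of 30 days before consent plus up to 14 days of screening, 44 in all.

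Assumed: each patient's yearly rate λ follows a gamma distribution with mean m and shape k, and events are Poisson and stationary.

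With a = 335λ/365, the probability of entry is w(λ) = [1 − e^(−a) − a·e^(−a)] × e^(−44λ/365). Then:

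- expected 12-month count before = E[a(1 − e^(−a))·e^(−44λ/365)] / E[w]
- expected yearly rate after = E[λ·w] / E[w]

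| Assumed m per year | k = 0.7 | k = 1 | k = 4 |
|---|---|---|---|
| 1 | 2.97 to 2.11 (−29%) | 2.82 to 1.87 (−34%) | 2.49 to 1.29 (−48%) |
| 2 | 3.66 to 3.14 (−14%) | 3.48 to 2.91 (−16%) | 3.04 to 2.32 (−24%) |
| 3 | 4.18 to 3.84 (−8%) | 4.02 to 3.66 (−9%) | 3.60 to 3.21 (−11%) |
| 4 | 4.59 to 4.36 (−5%) | 4.48 to 4.25 (−5%) | 4.18 to 4.01 (−4%) |
| 5 | 4.92 to 4.77 (−3%) | 4.86 to 4.74 (−3%) | 4.76 to 4.77 (0%) |
| 6 | 5.19 to 5.10 (−2%) | 5.20 to 5.14 (−1%) | 5.33 to 5.47 (+3%) |

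The fall vanishes at high rates because the 12-month history contains 30 days that cannot hold an event. If history is divided by the 335 eligible days instead, each after/before ratio is multiplied by 335/365. The fall is then 12-13% at 4 per year and 8-11% at 5. The SAP does not say which denominator applies.

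**3. What the P-value would show.** The SAP names no test for this table, so a paired t-test (two-sided 5%, n = 139) was assumed. With no drug effect and both periods annualised, simulation with k = 1, 2 or no heterogeneity gives a significant fall in 99.6-100% of trials at 1 per year, 63-98% at 2, 26-38% at 3, 5-12% at 4 and 0.5-6% at 5. On raw 12-month against 24-week counts, it was significant in every run of every scenario.

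**4. Definitions side by side.** A steroid course shorter than 3 days can count in history but not in the on-study steroid limb. An asthma hospitalisation without steroids counts on study but not under criterion 4. These pull in opposite directions, and the documents give no frequencies, so the net effect is unknown.

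**5. Background therapy.** With only 3 months on high-dose ICS plus LABA required, up to about 12 − 3 = 9 of the 12 history months may predate it. How often that happens is not stated.

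**The case against.** The best defence is that the trial never claims this comparison as an endpoint. The secondary objective is to assess effectiveness, its endpoints are all on-study measures, there is no hypothesis, and Section 6.4 admits the missing control and promises descriptive presentation. That stands for the endpoints: the annualised on-treatment rate and the time to first exacerbation are untouched. It does not cover Table 14.2.1.3, because a P-value on a before/after contrast is inferential. SAP Section 1 lets the SAP supersede the protocol, but no SAP text describes or justifies this addition.

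A reader might go further in three ways that the documents do not support:

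- **That the entry rules guarantee a fall.** They do not. On a 365-day scale the expected fall is near zero at about 5 per year and can reverse at 6, and the source rate is unknown. Only raw counts over unequal windows make a fall near certain, and that is a fault of the table, not of the inclusion criteria.
- **That every difference favours the drug.** The hospitalisation limb is wider on study, which works the other way.
- **That patients typically had their qualifying events before step-up, and so do not match the Section 4.2 population "who remain uncontrolled on high doses of ICS plus LABA".** Such a patient is eligible, but nothing shows this is common. Criteria 2 and 3 also require a severe asthma diagnosis for at least 12 months and FEV1 below 80% predicted at screening, and a physician must have prescribed the drug.

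**Conclusion.** The concern holds for SAP Table 14.2.1.3 and for the rationale's wording on reduction; it is not a fault in the inclusion criteria or the protocol endpoints. With selection on at least 2 prior events, no control and no adjustment, a fall from history cannot be attributed to benralizumab.

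Selection alone could account for an annualised fall of 29-48% at an assumed 1 per year, 14-24% at 2, 8-11% at 3, 4-5% at 4, and 3% to none at 5, with a possible small rise at 6. These figures rest on a stationary gamma-Poisson model with shape 0.7 to 4, and the rates are assumptions throughout. The 54% from unequal windows needs only a constant rate and all patients included in both means. The effects of the differing definitions and of earlier background therapy cannot be sized from the documents. The point should be fixed before reporting.

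**What to change.** 1. In Table 14.2.1.3, remove the P-value and the before/after contrast. Keep the on-treatment annualised rate as the endpoint, and show prior exacerbations only as a baseline characteristic. If Figures 14.2.2 and 14.2.3 plot the pre-study period, treat them likewise.
2. Reword the synopsis rationale so that the study describes the exacerbation rate on benralizumab.
3. Add to Section 6.4 that no reduction against history will be attributed to treatment, because patients were selected on that history.
4. If a descriptive contrast is kept, annualise both periods, state the history denominator, and label the contrast uncontrolled and subject to regression to the mean.

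Items 1 to 3 cost a few sentences and one shell, with no extra patients or visits. The sponsor gives up a favourable before/after claim.

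Applying one event definition to both periods, or restricting history to time on high-dose ICS-LABA, is not cheap. It needs dated, event-level history. Listing 16.2.1.1 shows prior exacerbations only as Yes or No, the sources cited for Table 14.2.1.3 are the exacerbation listings rather than that history listing, and Section 6.6 requires prior treatment to be recorded only for the 3 months before consent. The SAP's disposition footnote already reports 124 completions, so missing history may not be recoverable. Do this only if the data exist.
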